All patients will be required to have a current diagnosis of nAMD or DME with at least one eye eligible for 6-mg faricimab IVT injection, at the discretion of the retina specialist. Both previously treated and treatment-naive patients will be eligible for enrollment. Only one eye will be selected as the study eye. If both eyes are eligible, the investigator will determine which eye will be selected for study treatment (study eye).

The same retina specialist may act as the Principal Investigator and the HCP using the PFS configuration to administer faricimab. Alternatively, a sub-investigator may perform the duties of the HCP.

DISCLOSURE STATEMENT

This is a single-group device feasibility study that is not masked.

NUMBER OF PARTICIPANTS

Approximately 35 evaluable patients with nAMD or DME will be enrolled in this study.

6-mg Faricimab Prefilled Syringe—F. Hoffmann-La Roche Ltd 7/Protocol GR43742, Version 1 Note: "Enrolled" means a participant's or their legally acceptable representative's agreement to participate in a clinical study following completion of the informed consent process. Potential participants who are screened for the purpose of determining eligibility for the study but do not participate in the study, are not considered enrolled, unless otherwise specified by the protocol.

STUDY TREATMENT

The investigational medicinal product for this study is 6-mg faricimab PFS.

Patients will receive a single IVT injection of 0.05 mL of the 120-mg/mL faricimab (6-mg dose) formulation delivered via PFS with a co-packaged injection filter needle.

DURATION OF PARTICIPATION

[figure not shown]
The total duration of study participation for each patient is expected to be approximately 7 days.

INDEPENDENT DATA MONITORING COMMITTEE

An independent Data Monitoring Committee (iDMC) will not be used.

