4.1.2 Overview of Study Design and Procedure

A study schema is provided in Section 1.2 (see Figure 1). The schedules of activities are provided in Section 1.3 (see Table 1 and Table 2).

The study will be set up to enable usability (human factors [HF]) observations related to the use of the PFS configuration. This will be performed by the two HF observers who will be present at the study sites to observe each injection procedure. In the 30 days prior to (or including) Day 1, patients will be screened for their eligibility to participate in the trial.

As part of the information package sent in preparation for the study, each clinical study site will be provided with the IFU. Approximately 3 days prior to Day 1, HCPs will be expected to familiarize themselves with the documentation in advance and will be asked to confirm that they have read the IFU by signing an acknowledgement on Day 1. The HF observer and the additional observer will not provide a demonstration or training to HCP participants.

The HF observers will pre-brief the HCPs prior to the HF observations. When the patient is ready, the HF observers will be introduced to the patient in the administration room. The HF observers will be positioned such that they can clearly observe the entire preparation and administration process. The HCP team (i.e., retina specialist alone or retina specialist with assistant/technician, as per local procedure) will be asked to open the folding box only when the HF observers are present and to perform all preparation and administration steps in view of the HF observers. The PFS configuration should be prepared for use immediately prior to the injection, as described in the IFU. The HF observers will remain at a distance specified by the HCPs or facility and will not interrupt or interfere with the procedure. The HF observers will document HCP's performance using an assessment checklist and all administration procedures will be recorded on video to facilitate subsequent HF analysis of observations.

HF observers will ask for good visibility of all activities. To enable assessment of dose setting accuracy, HCPs will be asked to pause briefly during every procedure in order to turn and show the set dose to the observers for a closer look and brief video recording.

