4.4 END OF STUDY DEFINITION

A patient is considered to have completed the study if he or she has completed all phases of the study, including the safety telephone call 7 days after administration of the PFS injection.

The end of this study is defined as the date when approximately 35 patients have received injections, all HCP participants have completed their interviews with the HF observers, and the 7-day (\pm 1 day) reporting period after the PFS injection in the last patient has passed. It is expected that the duration of the investigation (length of study plus enrollment period) will be approximately 1.5 months.

In addition, the Sponsor may decide to terminate the study at any time.

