4.5 DURATION OF PARTICIPATION

The total duration of study participation for each patient is expected to be approximately 7 days.

5. STUDY POPULATION

Approximately 35 patients with nAMD or DME will be enrolled in this study.

Prospective approval of protocol deviations to recruitment and enrollment criteria, also known as protocol waivers or exemptions, is not permitted.

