5.1 INCLUSION CRITERIA

5.1.1 Inclusion Criteria for Health Care Providers

Criteria necessary for a retina specialist to participate in the clinical in-use study are the following:

- Valid medical license to practice in the United States
- Previous experience performing faricimab IVT injections using the vial and syringe procedure

Note that only the retina specialist or suitably-qualified retina fellows are allowed to perform the injection.

- Ability to pre-screen and recruit patients with nAMD or DME indicated for faricimab IVT therapy within a reasonable time frame (≤30 days)
- Ability to schedule the required baseline examinations and faricimab PFS injection procedures, and undergo clinical in-use evaluation within a relatively short time frame (≤7 days)

All additional HCPs (i.e., retina specialists nurses, assistants, or technicians) involved in the faricimab PFS preparation or injection procedure will be included in the study observations and the post-procedure interviews. All participating retina specialists and additional HCPs will be asked to sign an informed consent form regarding the observations to be conducted before commencing with injection preparation.

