7.2 PATIENT DISCONTINUATION OR WITHDRAWAL FROM THE STUDY

A patient may withdraw from the study at any time at his or her own request or may be withdrawn at any time at the discretion of the investigator for safety, behavioral, compliance, or administrative reasons.

The primary reason for discontinuation from the study should be documented on the appropriate eCRF. If a patient requests to be withdrawn from the study, this request must be documented in the source documents and signed by the investigator.

The patient will be permanently discontinued both from the study treatment and from the study at that time.

If a patient withdraws consent from the study, the Sponsor may retain and continue to use any data collected before withdrawal of consent. Patients who withdraw from the study will be replaced.

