7.3 PATIENTS LOST TO FOLLOW-UP

A patient will be considered lost to follow-up if he or she repeatedly is unable to be contacted by the study site.

The following actions must be taken if a patient fails to be contactable by the study site:

- The site must attempt to contact the patient and reschedule the missed visit as soon as possible and counsel the patient on the importance of maintaining the assigned visit schedule. If the patient is unable or unwilling to comply with study visits, site personnel should assess reasons the patient is unable or unwilling to participate, and determine if there are ways to support patient participation.
- Before a patient is deemed lost to follow-up, the investigator or designee must make every effort to regain contact with the patient (when possible, three telephone calls and, if necessary, a certified letter to the patient's last known mailing address or local equivalent methods). These contact attempts should be documented in the patient's medical record.
- In the event that the patient continues to be unreachable, he or she will be considered lost to follow-up and will be withdrawn from the study.

8. STUDY ASSESSMENTS AND PROCEDURES

Written informed consent for participation in the study must be obtained from the patients before performing any study-related procedures (including screening evaluations). Informed Consent Forms for enrolled patients and for patients who are not subsequently enrolled will be maintained at the study site. Informed Consent Forms for the HCPs participating in the HF observations will be collected and maintained by the HF observers during their visits at the study sites, and need to be signed before commencing to unpack and prepare the device for use.

Study procedures and their timing are summarized in the schedule of activities (see Section 1.3). Protocol waivers or exemptions are not allowed.

Urgent safety concerns should be discussed with the Sponsor immediately upon occurrence or awareness.

Adherence to the study design requirements, including those specified in the schedule of activities, is essential and required for study conduct.

All screening evaluations must be completed and reviewed to confirm that potential patients meet all eligibility criteria. The investigator will maintain a detailed record of all

patients screened to document eligibility or record reasons for screening failure, as applicable.

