9.2 SAMPLE SIZE DETERMINATION

Because the study aims to assess the safety of 6-mg faricimab PFS and no formal hypothesis testings are planned, there are no formal statistical considerations or analysis plan used to determine sample size. With approximately 12 patients per HCP team and at minimum three teams of HCPs, approximately 35 patients (at minimum 30 patients) with either nAMD or DME will enable evaluation of the safety of the 6-mg faricimab PFS per intended use.

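### Does the rule that withdrawn patients are replaced fail for patients who have already been injected and observed?

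*Protocol*

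**What the plan says.** Protocol Section 7.2 allows withdrawal at any time, lets the Sponsor keep data collected before consent is withdrawn, and ends with "Patients who withdraw from the study will be replaced". Section 7.3 says of a patient who stays unreachable that "he or she will be considered lost to follow-up and will be withdrawn from the study".

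The target is worded in three ways:
- Synopsis: "Approximately 35 evaluable patients with nAMD or DME will be enrolled in this study"
- Section 5: "Approximately 35 patients with nAMD or DME will be enrolled in this study"
- Section 4.4: "The end of this study is defined as the date when approximately 35 patients have received injections"

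Section 9.2 gives about 12 patients per team and at least three teams, and says "approximately 35 patients (at minimum 30 patients) with either nAMD or DME will enable evaluation of the safety".

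Two further passages bear on timing. Section 5.1.1 asks that the retina specialist be able to schedule baseline examinations and injections and "undergo clinical in-use evaluation within a relatively short time frame (≤7 days"). Section 4.1.2 has the team "open the folding box only when the HF observers are present".

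**The concern.** The primary objective concerns the health care providers. Observation, video and interview all take place on Day 1, and only two telephone calls follow. A patient who withdraws before the injection has contributed nothing to that objective; one who withdraws afterwards has contributed everything except safety follow-up. Section 7.2 treats both alike, and the undefined word *evaluable* does not tell a site which of them still counts towards 35.

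Read literally, the rule would have an injected and observed patient replaced. Section 9.2 appears to tolerate five losses already. A loss noticed at the last call would often come after the roughly one-week period of injections at that site, so the human factors observers might have to return, or another team might take the replacement and alter the split of about 12 per team. At stake would be a few injections beyond the planned number and an inconsistent rule across sites.

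**Working it through.** **Inputs.** From Section 9.2: about 12 patients per team, at least 3 teams, target about 35, minimum 30. From Section 5.1.1: the 7-day scheduling ability. From Table 2: calls on Day 3 (±1) and Day 7 (±1), with the injection on Day 1. From Section 4.4 and Appendix 3: the last contact 7 (±1) days after the injection. The protocol states no loss rate; 1%, 5% and 10% after injection are assumptions.

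**The plan's own figure.** 12 × 3 = 36, which agrees with about 35. There is no power calculation to reproduce, since Section 9.1 plans no test.

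**Does replacement conflict with the minimum of 30?** The margin is 35 − 30 = 5 patients, or 5/35 = 14.3%. Replacement can only raise the number with full follow-up, so it cannot breach a floor. The margin suggests replacement is seldom needed; it does not make the rule inconsistent.

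**Does replacement conflict with the 7 days?** Let d be the day of a 7-day injection period at a site.
- Table 2 numbering puts the last call on day d + 6 (±1). For d = 1 this is days 6 to 8, for d = 2 days 7 to 9, and for d = 3 days 8 to 10. The call is certain to fall outside from the third day on.
- Counting 7 days after the injection, as in Section 4.4 and Appendix 3, puts it on day d + 7 (±1). For d = 1 this is days 7 to 9, and for d = 2 days 8 to 10. The call is certain to fall outside from the second day on.

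So a late loss usually does surface after such a period. But the criterion describes what a retina specialist must be able to arrange. It does not bar a later injection, and the study schema allows injections on different calendar days for different teams and patients. A withdrawal may also surface at the first call, which under Table 2 falls on days 2 to 4 for d = 1, inside the period.

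**Extra injections under literal replacement.** To reach 35 with full follow-up at loss rate p, the expected extra number is 35/(1 − p) − 35.

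**Risk without replacing injected patients.** Falling below 30 needs at least 6 losses: P(X ≥ 6) with X ~ Bin(35, p).

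| Assumed loss p | Extra injections | P(fewer than 30 with full follow-up) |
|---|---|---|
| 1% | 0.4 | <0.001% |
| 5% | 1.8 | 0.7% |
| 10% | 3.9 | 13% |

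**Effect on safety precision.** The protocol plans no confidence bound; this one only shows scale. With no event among n patients, the one-sided 95% upper bound is 1 − 0.05^(1/n): 8.2% at n = 35, 8.7% at 33, 9.2% at 31 and 9.5% at 30. Replacing 2 to 4 injected patients (33 or 31 back to 35) therefore gains 8.7 − 8.2 = 0.5 to 9.2 − 8.2 = 1.0 percentage points.

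**The case for a change.** The best case for a change is that a replacement rule and an enrolment count belong in the protocol and not in an analysis plan, and that one sentence would settle both. Loss to follow-up is declared only after repeated contact attempts, so for the last patients the duty to replace could arise when the end-of-study conditions of Section 4.4 are already met. Two observers must attend every injection. Taking the periods in sequence, 30 days of recruitment, 7 of injections and 7 of follow-up make 44 days, against an expected duration of about 1.5 months (about 45 days). That leaves little room for a second observer visit.

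Part of this stands. Section 7.2 does not say whether injected patients are meant, *evaluable* has no definition in the protocol, and a late replacement would be awkward to arrange. But the 1.5 months is an expectation, not a limit, and every target is approximate. Applying the sentence to loss to follow-up is itself an inference from Section 7.3. Replacing an injected patient who lacks 7-day data is also defensible: Section 9.2 ties the sample size to evaluating safety, and Section 4.4 requires the Day 7 call for completion. Counting patients as injected and observed would be equally reasonable. A set of evaluable patients is commonly defined in an analysis plan, which is not at hand here.

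**Conclusion.** No change to the plan follows. The wording is loose, but it contradicts neither the minimum of 30 nor the scheduling criterion. If sites replace injected patients, the study gives about 0.4 to 3.9 more observed injections than 35, and the safety data gain slightly. If they do not, about 0 to 4 patients of 35 lack complete follow-up, and the chance of falling below 30 is 0.7% at 5% loss and reaches 13% only at 10%. All adverse events collected are summarized either way (Section 9.3), data from before withdrawal of consent may be kept, and no hypothesis is tested, so neither reading makes a result or conclusion wrong. This rests on the assumed loss rates of 1% to 10% and on independent losses. Whether to refill a patient who was observed but lacks the last call is a fair trade-off that the sponsor and sites can settle during conduct.

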7.3 PATIENTS LOST TO FOLLOW-UP

A patient will be considered lost to follow-up if he or she repeatedly is unable to be contacted by the study site.

The following actions must be taken if a patient fails to be contactable by the study site:

- The site must attempt to contact the patient and reschedule the missed visit as soon as possible and counsel the patient on the importance of maintaining the assigned visit schedule. If the patient is unable or unwilling to comply with study visits, site personnel should assess reasons the patient is unable or unwilling to participate, and determine if there are ways to support patient participation.
- Before a patient is deemed lost to follow-up, the investigator or designee must make every effort to regain contact with the patient (when possible, three telephone calls and, if necessary, a certified letter to the patient's last known mailing address or local equivalent methods). These contact attempts should be documented in the patient's medical record.
- In the event that the patient continues to be unreachable, he or she will be considered lost to follow-up and will be withdrawn from the study.

8. STUDY ASSESSMENTS AND PROCEDURES

Written informed consent for participation in the study must be obtained from the patients before performing any study-related procedures (including screening evaluations). Informed Consent Forms for enrolled patients and for patients who are not subsequently enrolled will be maintained at the study site. Informed Consent Forms for the HCPs participating in the HF observations will be collected and maintained by the HF observers during their visits at the study sites, and need to be signed before commencing to unpack and prepare the device for use.

Study procedures and their timing are summarized in the schedule of activities (see Section 1.3). Protocol waivers or exemptions are not allowed.

Urgent safety concerns should be discussed with the Sponsor immediately upon occurrence or awareness.

Adherence to the study design requirements, including those specified in the schedule of activities, is essential and required for study conduct.

All screening evaluations must be completed and reviewed to confirm that potential patients meet all eligibility criteria. The investigator will maintain a detailed record of all

patients screened to document eligibility or record reasons for screening failure, as applicable.

Medical history and baseline conditions, including clinically significant diseases, surgeries, reproductive status, and smoking history will be recorded at baseline. Any medications (including over-the-counter or prescription medicines, vaccines, vitamins, and/or herbal supplements) used by the patient within 7 days prior to initiation of study treatment will be recorded at baseline. Demographic data, including age, sex, and self-reported race or ethnicity, will also be recorded. At the time of each follow-up, an interval medical history should be obtained and any changes in medications and allergies should be recorded.

HF observations will be conducted by an HF specialist vendor, who will audio- and video-record the observations and will record their observations on prepared paper observation forms in ink (hardcopies). These are original documents and will be handled, maintained, and archived by the HF specialist vendor. Similarly, the original digital recorded interview sessions will be maintained and archived by the HF specialist vendor, as well as the HCP Informed Consent Forms. All information managed by the HF specialists must be traceable to these source documents and source records.

8.1 EFFICACY ASSESSMENTS

No efficacy assessments will be performed during this study.

8.2 SAFETY ASSESSMENTS

8.2.1 Ocular Assessments

IOP will be measured in the study eye predose on Day 1.

Following study treatment, patients will remain at the clinic for approximately 30 minutes.

Finger-counting test followed by hand motion and light perception tests (when necessary) will be performed within approximately 15 minutes post-study treatment in the study eye.

IOP will be measured in the study eye after treatment. If there are no safety concerns following the study treatment, the participant will be allowed to leave the clinic. If the IOP value is of concern to the Investigator, the participant will remain in the clinic and be managed in accordance with the Investigator's clinical judgement. The same device must be used to measure pretreatment IOP and posttreatment IOP.

If applicable, the adverse event and the adverse event treatment (if applicable) will be reported on the appropriate eCRFs.

See Table 2 for the schedule of assessments performed during the study.

If warranted during the study duration (7 days), patients will be asked to return to the clinic as soon as possible for an unscheduled safety assessment visit (see Appendix 9).

8.2.2 Pregnancy Testing

The schedule for pregnancy testing for enrolled female patients is outlined in Table 2 of Section 1.3 and will be conducted as outlined in Appendix 6.

8.3 ADVERSE EVENTS, SERIOUS ADVERSE EVENTS, AND OTHER SAFETY REPORTING

The definitions of adverse event and serious adverse event can be found in Appendix 2.

Adverse events will be reported by the patient (or, when appropriate, by a caregiver, surrogate, or the patient's legally authorized representative).

The investigator and any qualified designees are responsible for detecting, documenting, and recording events that meet the definition of an adverse event or serious adverse event and remain responsible for following up adverse events that are serious, are considered related to the study treatment or study procedures, or caused the patient to discontinue the study (see Section 7).

8.3.1 Time Period and Frequency for Collecting Adverse Event and Serious Adverse Event Information

After informed consent has been obtained but prior to initiation of study drug, only serious adverse events caused by a protocol-mandated intervention should be reported (see Appendix 2). All other medical occurrences deemed significant by the investigator that begin before the start of study treatment but after obtaining informed consent will be recorded on the relevant medical history eCRF, not the Adverse Event eCRF.

All adverse events (ocular and non-ocular) will be reported from the start of treatment until Day 7 after the faricimab PFS injection procedure (see Section 1.3).

All serious adverse events will be recorded and reported to the Sponsor or designee immediately and under no circumstance should this exceed 24 hours, as indicated in Appendix 2. The investigator will submit any updated serious adverse event data to the Sponsor within 24 hours of it being available.

The 7-day reporting period has been determined based on the expected timing of potential procedure-related events. In addition, all patients will be instructed to immediately contact their retina specialist if their eye becomes red, sensitive to light, painful, or develops a change in vision any time after the injection, including after the reporting period ends.

Investigators are not obligated to actively seek adverse event or serious adverse event information after conclusion of study participation. However, if the investigator learns of any serious adverse event, including a death, at any time after a patient has been

6-mg Faricimab Prefilled Syringe—F. Hoffmann-La Roche Ltd 27/Protocol GR43742, Version 1

discharged from the study, and he or she considers the event to be reasonably related to the study treatment or study participation, the investigator must promptly notify the Sponsor.

8.3.2 Method of Detecting Adverse Events and Serious Adverse Events

The method of recording, evaluating, and assessing causality of adverse events and serious adverse events and the procedures for completing and transmitting serious adverse event reports are provided in Appendix 2.

Care will be taken not to introduce bias when detecting adverse events and/or serious adverse events. Open-ended and non-leading verbal questioning of the patient is the preferred method to inquire about adverse event occurrences.

